Lung Cancer Surgery: Decisions Against Life Saving Care - The Intervention

NCT01687738

Protocol Date: May 13, 2011

Most Recent IRB Approval Date: March 29, 2016

Lung Cancer Surgery: Decisions Against Life Saving Care - The Intervention

STATISTICAL ANALYSES

Outcome Measures

Primary Outcome. Whether or not patients undergo lung resection surgery represents the main study outcome. We will conform to the 4 month standard used in the SEER database. To ascertain the result, we will first call patients' physicians to determine whether surgery occurred within the designated time frame. Given the possibility that individual patients could seek other opinions and receive surgical care elsewhere, when appropriate, we will ask the patient, or a family member (if the patient is dead or unavailable), whether surgery was performed by someone other than the index physician. If surgery has not occurred, we will ask for reasons. Through appropriate consent, we will retain the option of confirmatory medical records review. For secondary analyses, we will record surgeries that occur beyond the 4 month threshold.

Secondary Outcomes.

1. One year, post-enrollment survival in surgical and non-surgical groups
2. Satisfaction of patients that received interventions compared to those who did not
3. Patients' perceptions of communication for those patients that received intervention compared to those who did not
4. SF-12 scores at baseline, 6 months post-enrollment and 12 months post enrollment

6. Data Analysis:

Our current plan includes:

Descriptive statistics (means, standard deviations, frequencies, proportions, correlations, and graphical displays) will be computed for all study variables at baseline and post-baseline. The distribution of all outcome variables will be assessed to determine if distributional assumptions are valid. Descriptive statistics will be obtained for all the variables overall and by race and site. Statistical methods for addressing each of the specific aims of the study are detailed in this section. Since several statistical tests are planned, there is the possibility of incurring spurious results if we do not correct for multiple comparisons. All tests are based on a 2-sided alpha of 0.05.

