The main outcome of interest is whether patients undergo surgery is a dichotomous variable, either yes or no. We will compute proportions to estimate the probability of surgery for blacks and whites and compute 95% confidence intervals for the proportions. Since the main outcome is dichotomous, logistic regression for clustered data (clustered within sites) using multiple predictors will be used to assess the simultaneous effect of predictors on the outcome.

Specific Aim 1. To maximize surgical rates for all patients with stage I and II, non-small cell lung cancer who do not have absolute contraindications for lung resection surgery.

hypothesis 1a. a cancer communicator who utilizes active listening and teach-back methods during discussions about lung cancer surgery with newly diagnosed, early stage patients will increase the rate of surgery in Caucasian and African-American patients who do not suffer absolute contra-indications for lung cancer surgery compared to usual care

The primary outcome variable, surgery yes or no, will be compared in the control group randomized to usual care, to the intervention group randomized to the cancer communicator. Bivariate analyses will be performed using the surgical outcome as the dependent variable. Independent variables in these analyses will include important group, demographic variables

such as age, race, marital status, household income, health insurance, gender, and education as well as measures of trust, patient satisfaction, functional status, self-reported health, comorbid illness, perceptions of communication, and the communication intervention. We will use bivariate analyses, including correlations and chi-square tests of association, to make preliminary assessments of the relationships between study variables, overall and by race.

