
hypothesis 1b. the communication intervention will be more effective in patients who score lower in measures of health literacy

Using the logistic regression analyses for clustered data as noted above, the interaction effects of health literacy, S-TOFHLA scores, and intervention group will be tested in all models. . S-TOFHLA scores will be tested as a continuous variable and also, separately, as a dichotomous variable comparing those categorized as inadequate or marginal literacy with those categorized as adequate literacy [103]. Cumulative pre-intervention surgical rates will be compared at all sites with post-intervention rates using Pearson's chi-square test. Post-intervention rates will be compared using test of proportions and changes in proportions from baseline will be compared between surgical and nonsurgical groups using appropriate methods. To determine if the post-intervention rate approaches maximal surgical rates, we will identify patients with high risk co-morbidities, above the age of 80, and need for pneumonectomy or multiple lobectomy in the "no surgery group", subtract this sum from the denominator then re-calculate the surgical rate. We will analyze the secondary specific aim, To measure the effect of the intervention on patients' perceptions of communication and satisfaction with care, by dichotomizing these variables and replacing surgery as the dependent variable in chi-square and logistic regression models as described under the specific aim above.

Specific Aim 2. To reduce the documented difference in lung resection surgery and mortality between African-American and White patients with early stage, non-small cell

lung cancer.

hypothesis 2a. giving physicians who make lung cancer surgery decisions data relating co-morbidity to surgical outcomes will reduce racial differences in surgery

hypothesis 2b. using a real time lung cancer registry to provide physicians race-specific feedback about their surgical treatment of early stage lung cancer patients will reduce racial differences in surgery

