The SF-12 physical and mental component scores will be converted to 0 – 100 scales and utilized as the dependent variable. Baseline scores will be compared first to 6 month scores then 12 month scores using paired t-tests. Generalized linear mixed models for repeated measures data will be constructed in a similar manner as the logistic regression models described above; however, surgical status, race, and comorbid conditions will be forced predictors in these model.

Note that interim analyses regarding specific aims 1 and 2 will be performed at the end of study year 2 then annually. If statistically significant benefits in care are documented on surgical rates and reduction in disparities, the study will be terminated and workshops and individual training sessions of the communication methodologies will be initiated for the care teams at all the study sites.

7. Sample Size

Power computations are computed for post-intervention comparison of proportions. The project anticipates enrolling 496 patients into the study due to constraints on budget, patient availability, and study duration. Thus, we compute the minimal effect size we can detect with statistical power of 80% for our primary aim, AIM 1, using the specified sample size. In computing the effect size, we specify our main outcome as the probability of undergoing surgery for all patients post-baseline as compared to the probability for all patients in the previous study because all groups will receive the data registry and feedback interventions.

Let p_1 be the proportion all patients who undergo surgery in the present study and $p_0 = 0.63$ be the proportion of patients who underwent surgery in the previous study. Using a one-sample test of proportion with 496 subjects overall and significance level of 0.05, we have 80% power to detect a minimally important difference (increase) in surgical rate of $p_0 = 0.63$ to $p_1 = 0.69$. With a sample size of 159 for blacks, we have 80% power to detect an overall increase from $p_0 = 0.55$ (as measured in the previous study) to $p_1 = 0.66$ with significance level of 0.05. With a sample size of 337 for whites, we have 80% power to detect an overall increase from $p_0 = 0.66$ (as measured in the previous study) to $p_1 = 0.73$ with significance level of 0.05.

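### The SAP raises multiplicity but sets every test at two-sided 0.05, with no correction, no testing order and no single primary test

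*SAP*

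**What the plan says.** The opening of SAP section 6 (Data Analysis) contains two adjacent sentences. The first is "Since several statistical tests are planned, there is the possibility of incurring spurious results if we do not correct for multiple comparisons". The second is "All tests are based on a 2-sided alpha of 0.05". Neither document returns to the subject.

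The plan does rank some things. Under Outcome Measures, "Whether or not patients undergo lung resection surgery represents the main study outcome", judged at 4 months, and four secondary outcomes follow. Section 7 calls Aim 1 the primary aim.

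Below the level of the aim there is no ranking. Aim 1 carries two labelled hypotheses:

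- The randomised comparison: "hypothesis 1a. a cancer communicator who utilizes active listening and teach-back methods" is expected to raise surgery rates against usual care.
- An interaction: "hypothesis 1b. the communication intervention will be more effective in patients who score lower in measures of health literacy". For this one, "S-TOFHLA scores will be tested as a continuous variable and also, separately, as a dichotomous variable".

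Aim 2 carries 2a, 2b and 2c. The first of these reads "hypothesis 2a. giving physicians who make lung cancer surgery decisions data relating co-morbidity to surgical outcomes will reduce racial differences in surgery". Aim 4 carries 4a and 4b, each at 6 and 12 months. Aim 3 has no labelled hypothesis.

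Section 7 then bases power on a one-sample test of all enrolled patients against the rate in the previous study (0.63 to 0.69, 496 patients), where "we have 80% power to detect a minimally important difference (increase) in surgical rate". It repeats this for Black patients (159) and White patients (337), each at 0.05.

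**The concern.** The SAP names a risk and then adopts a rule that leaves it in place. Surgery yes/no is the endpoint for 1a, 1b, 2a, 2b, 2c and Aim 3, so one primary outcome does not mean one primary test. A reader of the final report could not tell from the plan which surgery p-value was meant to decide the question. There are at least two candidates: the randomised comparison in 1a and the historical comparison in Section 7, the latter also in separate Black and White versions.

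The gap also reaches a decision about the trial. The end of section 6 provides for interim analyses of Aims 1 and 2 at the end of study year 2 and then annually, with termination on statistically significant benefit. Without a defined test, that rule has no defined input. The error from repeated looks is a separate matter and is not counted below.

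**Working it through.** **1. Reproduce the plan's own figure.** Inputs are from SAP section 7. The formula is the one-sample normal approximation, power = Φ[(p1 − p0 − 1.96·√(p0(1−p0)/n)) / √(p1(1−p1)/n)].

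- All: n = 496, 0.63 to 0.69. (0.06 − 1.96 × 0.02168) / 0.02077 = 0.843, power 80.0%.
- Black: n = 159, 0.55 to 0.66. (0.11 − 1.96 × 0.03945) / 0.03757 = 0.870, power 80.8%.
- White: n = 337, 0.66 to 0.73. (0.07 − 1.96 × 0.02580) / 0.02418 = 0.803, power 78.9%.

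The stated 80% is reproduced with a two-sided 0.05 for each test. One-sided testing gives 87% to 89% and does not match. So Section 7 uses the full, unshared 0.05 three times, and none of the three is the randomised comparison.

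**2. Count the named hypotheses.** 1a, 1b, 2a, 2b, 2c, 4a, 4b: seven. Section 6 serves 2a and 2b with one before/after contrast for the registry and feedback, so six distinct tests is also a fair count.

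**3. Chance of at least one false positive.** The documents state no family-wise rate. With k independent tests at 0.05 and all nulls true, it is 1 − 0.95^k.

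- k = 7: 1 − 0.6983 = 30.2%.
- k = 6: 1 − 0.7351 = 26.5%.

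The bound for seven tests under any dependence is 7 × 0.05 = 35%.

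**4. Allow for correlation.** The surgery hypotheses share an outcome and patients, so independence is unlikely. The documents give no correlation between tests, so a range is assumed. Simulating k two-sided z-tests with a common correlation (500,000 replicates) gives:

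| Common correlation | k = 7 | k = 6 |
|---|---|---|
| 0 | 30% | 27% |
| 0.3 | 27% | 24% |
| 0.5 | 23% | 21% |
| 0.7 | 18% | 16% |

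**5. What the count leaves out.** It treats 1b as one test although two codings are planned, and 4a and 4b as one each although there are two time points. It also omits the bivariate tests and the backward elimination from a model of up to 30–35 terms.

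**The case against.** The strongest reply is that the plan already has a hierarchy: one primary outcome, four secondary outcomes, a primary aim, and bivariate and chi-square work described as preliminary. Under 1a the primary outcome is explicitly compared between the randomised groups. Taken alone, as one fixed-sample test, 1a keeps its 5% error. All of this stands. It would be wrong to say that the plan ranks nothing, or that the chi-square and the GEE model are rival primary tests of 1a. But the hierarchy stops at outcome and aim. It does not choose between 1a and 1b, and Section 7 defines the main comparison as a different one.

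A reader might also infer three stronger points that the documents do not support.

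- *That the SAP contradicts itself.* It says spurious results are possible without correction. It does not say that correction is required, so this is an unresolved caveat and not a contradiction.
- *That the false-positive chance is 43%.* That needs 11 tests (1 − 0.95^11 = 43.1%), for example by adding Aim 3 overall and in African-Americans and splitting 4a and 4b by time. Only seven hypotheses are named, and Aim 3's before/after comparison largely overlaps that for 2a and 2b.
- *That the 80% powers are false because a correction would lower them.* The SAP specifies no correction, so there is no set level at which to recompute them. Any split of 0.05 across the three tests would be the reader's own.

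Nor do the documents state that any single significant result counts as success. The one decision rule, for termination, asks for benefit on surgical rates and on disparities together.

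**Conclusion.** The concern holds in a limited form. Multiplicity is acknowledged, nothing is done about it, and no single test is designated primary. For the seven named hypotheses the chance of at least one false positive is about 30%. This assumes independent tests, all nulls true, and one test per hypothesis at 0.05. It is 26.5% if 2a and 2b are one contrast, and about 18% to 27% for seven tests with a common correlation of 0.7 to 0.3. These are family-wise rates and do not show that 1a itself is inflated. The multiple codings, time points, screening tests and interim looks lie outside the count and would push the overall rate up by an amount the documents do not allow one to fix.

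**What to change.** In SAP section 6, replace the blanket 0.05 sentence with a rule to this effect:

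- Hypothesis 1a (randomised communicator v usual care, surgery within 4 months) is the single primary test, at two-sided 0.05, using one named analysis, for example the site-adjusted model with group forced in.
- The other named hypotheses are either Holm-corrected as one secondary family or reported as exploratory; the SAP should say which.
- All remaining p-values, including the preliminary bivariate tests, are exploratory.

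If 1b stays in a corrected family, state which S-TOFHLA coding counts. In section 7, label the Black and White powers as uncorrected for multiplicity, and say that the three figures concern the historical comparison and not 1a.

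The cost is SAP wording and less favourable secondary p-values. No patients are added, and the level for 1a is unchanged. The change does not deal with the repeated interim looks, which need their own provision.

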The modeling approach will be to initially define as large a maximum model as possible using main effects only (initially no interactions). Preliminary analyses of similar data indicates that the sample size combined with a sufficient number of events (surgery yes) will allow upwards of 30-35 main effects to be included in the model with good reliability for estimation and inference. The generalized estimating equations (GEE) for binary outcomes will be used to fit logistic regression models for clustered data [102]. The primary outcome variable is binary, surgery yes or no, and outcomes of patients clustered within the same site (and/or MD) are expected to be correlated. GEE will allow fitting a logistic regression to the binary outcome while adjusting for the effect of clustering within the same site (and/or MD). As stated previously, independent variables in these analyses will include important demographic variables such as age, race, marital status, household income, health insurance, gender, and education as well as measures of trust, patient satisfaction, functional status, self-reported health, comorbid illness, perceptions of communication, and the communication intervention. The significance of each of the main effects while adjusting for all other effects from the maximum model will be assessed. A backwards elimination approach will, initially, remove effects with a p-value of greater than 0.10. This excludes selected predictors forced predictors into the model (forced predictors include group, comorbid illnesses and selected baseline scores). The reduced model will be refit. Variables have p-values greater than 0.05 will then be removed. The final reduced main effects model, including forced predictors will be refit. Selected interactions will be considered for inclusion into the final reduced main effects model. For the secondary outcomes, survival analysis techniques will be used to assess the one year, post-enrollment survival in surgical and non-surgical groups. Kaplan-Meier curves will be generated. Linear regression models for repeated measures (discrete) outcomes using GEE will be used to assess patient satisfaction of patients that received interventions compared to those who did not, for patients' perceptions of communication for those patients that received intervention compared to those who did not, and for SF12 scores at 6 months post-enrollment and 12 months post enrollment. Covariates will include baseline, group, and other covariates listed above.

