Specific Aim 3. To measure the effect of all elements of a multi-modal intervention that includes a cancer communication educator, data feedback, and a co-morbidity checklist on overall lung cancer surgery rates and rates for African-Americans.

To address specific Aim 3 we will first examine unadjusted relationships between race and clinical characteristics using chi-square analyses to obtain preliminary assessment of clinical characteristics that may be similar. A logistic regression model with binary outcome "undergo surgery or not undergo surgery" will be used to assess the effect of baseline scores, multiple clinical characteristics and patient race. Whether the effect of race remains constant across levels of clinical characteristics will be assessed in the logistic regression model using selected interaction terms of race x clinical characteristic. We will examine the direction and size of the interaction effects to help judge whether African-American patients undergo lung cancer surgery less often than Caucasian patients with similar clinical characteristics. We will repeat these analyses stratified by race to further examine predictors of differential effect. GEE with exchangeable correlation structure and generalized linear mixed models will be used to account for correlation within-physician. To measure the effect of the intervention, we'll examine before and after lung cancer surgery rates and control for the variables as noted in Specific Aim 1. To help control for the varying lengths of time before and after lung cancer surgery, we will include a length of time measure in our models as both a main effect and with selected interactions.

Specific Aim 4. To follow patients' functional status over time and explore the relationship of surgery, race, and co-morbid conditions on functional status.

hypothesis 4a. Individuals who undergo lung cancer surgery will experience better physical functioning at six months and 12 months than those who don't

hypothesis 4b. Individuals who undergo lung cancer surgery will experience better mental functioning at six months and 12 months than those who don't

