From the analysis of our previous study, we found that practically negligible correlation existed between subjects for the primary outcome, surgery yes or no. The correlations seen ranged from -0.002 to 0.01 when using GEE for clustered observations in the previous study. In other words, clustering had a negligible effect on the results in the previous study. As such, we can expect the same in the proposed study. Therefore, we feel there is little or no need for power and sample size computation based on clustered observations. However, we will still adjust for patients clustering within site and/or physicians in the logistic regression models using GEE described in the Data Analysis section.

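### The main GEE model is clustered on four sites with no variance method named; with the uncorrected robust SE and a z test, the false-positive rate is about 20%, not 5%

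*SAP*

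**What the plan says.** The Data Analysis section of the SAP opens with the rule "All tests are based on a 2-sided alpha of 0.05". For the primary outcome, surgery within 4 months, it states that "logistic regression for clustered data (clustered within sites) using multiple predictors will be used to assess the simultaneous effect of predictors on the outcome". The text under hypothesis 1a fits this model by GEE and allows clustering by site, by physician, or both. The Sample Size section repeats the open choice: "we will still adjust for patients clustering within site and/or physicians in the logistic regression models using GEE". The protocol's description of the study areas lists four sites.

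The same model is used in three ways:
- **Hypothesis 1a.** It gives the adjusted test of the communicator. Group is a forced predictor.
- **Predictor selection.** "A backwards elimination approach will, initially, remove effects with a p-value of greater than 0.10"; a second step then removes those above 0.05.
- **Hypothesis 1b.** "the interaction effects of health literacy, S-TOFHLA scores, and intervention group will be tested in all models".

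The only correlation structure named is under Aim 3: "GEE with exchangeable correlation structure and generalized linear mixed models will be used to account for correlation within-physician". That is a working correlation, not a variance estimator, and it is not carried to Aim 1. Neither document states how standard errors are computed, whether a small-sample correction applies, or which distribution gives the p-value.

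**The concern.** The robust variance commonly paired with GEE is estimated from the cluster totals, and its justification needs many clusters. With four it is usually too small and very variable, and the normal distribution is the wrong reference. Two analysts could both follow this SAP and test hypothesis 1a at a true level of 5% or of 20%.

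The affected results would be the adjusted test of the communicator, the literacy interaction, and the p-values that decide which covariates stay. Forcing group into the model keeps the term but does not protect its p-value. The SAP also allows the study to end on statistically significant benefit at interim looks without saying which test decides, so an inflated test could contribute to stopping.

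The Sample Size section reports correlations of -0.002 to 0.01 and calls clustering negligible. That bears on power. It does not bear on estimating a variance from four totals.

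**Working it through.** **Inputs from the documents.** Four sites (Protocol B); N = 496 and surgery rates 0.63 and 0.69 (SAP 7); two-sided 0.05 and 30–35 main effects (SAP 6); correlation -0.002 to 0.01 (SAP 7); 2007 registry counts 63, 141, 57 and 66, total 327 (Protocol C).

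**Assumptions.** Registry shares scaled to 496 (for example 141 × 496/327 = 214) give sites of 96, 214, 86 and 100. Overall surgery rate is 0.66; site correlation is 0 or 0.01; working correlation is independence.

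**The plan's own figure.** One-sample power for 0.63 to 0.69: [0.06 × √496 − 1.96 × √(0.63 × 0.37)] / √(0.69 × 0.31) = (1.336 − 0.946)/0.462 = 0.843, and Φ(0.843) = 0.80. This matches the stated 80% and confirms the two-sided reading. The plan gives no figure for the error rate of the GEE test.

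**Analytic check.** With K equal clusters and no correlation, the uncorrected robust z behaves like t(K−1) × √(K/(K−1)). For K = 4:
- Against z: P(|t(3)| > 1.96 × √(3/4)) = P(|t(3)| > 1.697) = 18.8%.
- Against t(3), critical value 3.182: P(|t(3)| > 2.756) = 7.0%.
- Variance × 4/3 with t(3): the factor cancels, giving 5%.
- SE × 4/3 with t(3): P(|t(3)| > 3.182 × √(4/3)) = P(|t(3)| > 3.675) = 3.5%.

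No correlation term enters, so the inflation exists at zero correlation.

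**Null simulations for the communicator effect** (5,000 trials per setting without covariates; 2,500 with 32 null covariates):

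| Method, four site clusters | No covariates | 32 covariates |
|---|---|---|
| Uncorrected robust SE, z | 18.8–20.6% | 20.8–21.8% |
| Uncorrected robust SE, t(3) | 7.3–8.1% | – |
| Robust variance × 4/3, t(3) | 5.1–5.9% | 5.7–6.6% |
| Model-based SE, no site terms | 5.0–5.6% | 6.1–6.3% |
| Site indicators, model-based SE | 4.9–5.7% | 6.0–6.3% |
| Site indicators, uncorrected robust SE, z | 18.8–20.5% | – |

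Model-based rows without covariates are at zero date-level correlation. The median ratio of robust to model-based SE was 0.73–0.75, with a 5th–95th percentile range of about 0.28 to 1.38. Repeating the robust z test at a surgery rate of 0.63, with equal or unequal sites, simple randomisation, 5 to 33 covariates, and exchangeable or independence working correlation, gave 18–22%.

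**Literacy interaction** (3,000 trials, score continuous or dichotomous, 30% low literacy assumed): robust z 19.2–21.2%; site indicators with model-based SE 4.5–5.4%.

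**Two-step elimination** (1,500 trials, 32 irrelevant predictors): robust z keeps 6.3–6.4 of them (about 6.4/32 = 20%), against 1.8 (5.5–5.7%) with site indicators and model-based SE. The final group test rejects in 22% against 5–6.5%.

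**If physicians are the cluster** (number not stated; 10, 20 and 40 assumed; 3,000 trials, robust z, no covariates): equal caseloads 8.5–9.1, 7.3–8.0 and 5.8–5.9%; very uneven caseloads 11.3–11.8, 9.2–9.4 and 8.3–8.9%. With 32 covariates the highest values are 13.4, 11.5 and 8.6%. A Mancl–DeRouen variance with t on K−1 df gave 3.5–6.4% without covariates.

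**Alternating recruitment dates.** The protocol alternates arms by date. With 1–3 patients per date assumed, date-level correlation of 0.01, 0.02, 0.05 and 0.10 moves site indicators with model-based SE to 5.1, 5.2, 5.9 and 6.5%.

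**Power of the valid options** (0.63 vs 0.75 assumed): site indicators 82–84%; variance × 4/3 with t(3) about 53%.

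Monte Carlo error is about 1 point or less, and about 2 points for the 20% rates at 1,500–2,500 trials.

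**The case against.** The 20% needs three choices together: site as the only cluster, an uncorrected sandwich SE, and a Wald z test. The SAP states only the first, and reopens it elsewhere. Physicians are a live reading, since the protocol's Data Feedback section says a few physicians per system deliver nearly all the care. Model-based SEs would hold about 5–6%.

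Nor is the error always upward. A robust score statistic on four clusters equals 4t²/(t² + 3) in terms of t(3), so it cannot exceed 4, against a critical value of 3.84. It rejects only when t² > 3 × 3.8415/(4 − 3.8415) = 72.7, that is |t| > 8.53, in 0.34% of trials (0.2–0.4% simulated).

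Finally, the SAP also plans unaffected unadjusted tests, such as "Post-intervention rates will be compared using test of proportions", and names no confirmatory test.

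All of this stands as a limit on the claim: the 20% is conditional. It does not remove the problem. Site is the only unit named where the main model is introduced, the robust Wald test is an ordinary way to run GEE, and nothing in the text excludes it. The score test is a second way in which robust inference on four clusters misses 5%. The SAP also describes its bivariate work under hypothesis 1a as preliminary and assesses significance in the adjusted model, so that model may well carry the conclusion.

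**Conclusion.** The concern holds, as a conditional statement. With four site clusters, the uncorrected robust SE and a z test, the nominal 5% test of the communicator has a true level of 19–22%, and the literacy interaction 19–21%. About one in five irrelevant predictors survives elimination, against about one in eighteen (1.8 of 32) with site indicators and model-based SEs. The result does not depend on correlation within sites and changes little with site sizes, working correlation or number of covariates. It rests on assumed surgery rates of 0.63–0.66 and, in the main runs, on registry-proportional sites.

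Under physician clustering the inflation is smaller, about 6–13% for an assumed 10 to 40 physicians, and nearly gone with 40 equal caseloads. Unadjusted comparisons of the arms are unaffected. This should be fixed before analysis.

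**What to change.** State the cluster unit, variance estimator and reference distribution for Aim 1, and say whether the adjusted or the unadjusted comparison is confirmatory.

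- **Preferred.** For the randomised comparison, the literacy interaction and the elimination steps, use logistic regression with three site indicators and model-based SEs. Do not pair site indicators with the uncorrected robust SE, which leaves the error at 19–21%.
- **If GEE on site is kept.** Use the model-based SE, or multiply the robust variance (not the SE) by 4/3 and refer to t on 3 df. The second option is valid but has about 53% power against 82–84% in the assumed scenario.
- **If physicians are the cluster.** Use a small-sample corrected variance such as Mancl–DeRouen with a t reference, or extend the Aim 3 physician mixed model to Aim 1. The mixed model was not simulated here.
- **Alternating dates.** If many patients of one arm enrol on the same date, check date-level correlation, because model-based SEs assume there is little.

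The cost is SAP wording and three more model parameters. No new data are needed.

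### The SAP's capacity of 30–35 main effects rests on the commoner outcome; the limiting count supports about 15–18, and the race-stratified and single-arm models have no smaller limit

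*SAP*

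**What the plan says.** Under hypothesis 1a (SAP section 6), the intention is to "define as large a maximum model as possible using main effects only", fitted as a GEE logistic regression that allows for clustering by site and/or physician. The stated capacity is that a "sufficient number of events (surgery yes) will allow upwards of 30-35 main effects to be included in the model", with reliability described as good. Fourteen predictors are named, counting the communication intervention itself. Selection follows: "A backwards elimination approach will, initially, remove effects with a p-value of greater than 0.10". After a refit the threshold tightens to 0.05. Group, comorbid illness and selected baseline scores are forced in, and the reduced model is refitted.

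SAP section 7 supplies the numbers: "The project anticipates enrolling 496 patients into the study due to constraints on budget". It takes surgery rates of 0.63 (previous study) to 0.69 (target) for all patients, and 0.55 to 0.66 for 159 Black patients.

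Two later sections carry the models into subsets. Specific Aim 3 states: "We will repeat these analyses stratified by race to further examine predictors of differential effect". It also adjusts its before-and-after comparison for the Aim 1 variables. Under hypothesis 2c, the SAP refers back to the Aim 1 regression models and then applies its analyses to communicator patients alone. No smaller limit on predictors is given in either place.

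**The concern.** The information in a logistic model is limited by the smaller of the two outcome groups. Which outcome is called the event is arbitrary: coding no surgery as 1 gives the same fit with the signs reversed. A capacity that depends on that label cannot be right, and here the label was put on the larger group.

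With too many parameters for the limiting group, log odds ratios are pushed away from zero, model standard errors come out too small, and null effects are rejected too often. The smallest samples in this plan are the race-specific ones, and those models are meant to inform the disparity aims.

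**Working it through.** **1. Reproduce the SAP's figure.** Inputs are N=496 and rates 0.63 and 0.69 (SAP section 7). The documents name no rule; 10 outcomes per parameter is an assumption.

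- With surgery: 496 × 0.63 = 312 and 496 × 0.69 = 342.
- Divided by 10: 31 and 34, which matches 30–35.

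**2. Use the limiting outcome, full sample.**

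- Without surgery: 496 × 0.37 = 184 and 496 × 0.31 = 154.
- Per parameter at the stated capacity: 184/30 = 6.1 down to 154/35 = 4.4.
- Capacity at 10 each: 18.4 and 15.4. The stated 30–35 is 30/18.4 = 1.6 to 35/15.4 = 2.3 times that.
- Other conventions: 31–37 parameters at 5 each, 10–12 at 15, and 8–9 at 20.

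**3. Subsets, enrolled patients only.**

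- Black patients, n=159: 159 × 0.45 = 72 and 159 × 0.34 = 54 without surgery, so about 5–7 parameters at 10 each and 11–14 at 5 each.
- With the 30% enrolment goal (Protocol section E.2), 0.30 × 496 = 149: 67 and 51 without surgery, again about 5–7.
- The 14 named predictors at one parameter each: 54/14 = 3.9 to 72/14 = 5.1 limiting outcomes per term. Race drops out within a stratum; with 13 terms this becomes 4.2–5.5.
- Communicator arm, 248 if allocation is 1:1 (the ratio is not stated): 77–92 without surgery, so about 8–9 parameters.

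**4. Size of the effect, by simulation.** The runs used ordinary logistic regression, independent covariates, no clustering, 5 or 8 modest real covariate effects, and a binary arm term with a log odds ratio of about 0.4–0.5. Ranges are across runs with slightly different settings.

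| Setting | Inflation of log odds ratio | Type I error |
|---|---|---|
| n=496, 33 terms, unreduced | about 8–10% | about 6–7% |
| n=496, after the 0.10-then-0.05 elimination | about 4–5% | 4.6% |
| n=159, 33 terms, unreduced | about 35–40% | 8–9% |
| n=159, 33 terms, after elimination | about 11–17% | 7–9% |
| n=159, 14 one-parameter terms | about 10% | about 6% |
| n=159, 7 terms | 7% | 4.7% |

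At n=496, inflation of 8% on a log odds ratio of 0.50 is 0.04, about one fifth of a standard error (0.04/0.215). What suffers more there is prediction: the calibration slope was 0.52 with 33 terms and 0.74 with 16.

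**The case against.** The strongest reply has four parts.

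- **The maximum model is only a starting point.** What is reported is the model left after elimination. This stands for the full sample, where elimination brings type I error to 4.6%. At n=159 it reduces the distortion without removing it, because the p-values that drive selection come from the overfitted model.
- **The 10-per-parameter rule is not in the documents.** This also stands. At 5 per parameter the full-sample model would just fit. Among Black patients, 30–35 exceeds the capacity under either rule.
- **The figure of 30–35 is a capacity for the full sample.** A reader might infer that all 30–35 effects will be refitted in 159 Black patients and take the 35–40% inflation as the plan's expected error. No section says so. The Aim 3 model is described separately, in terms of baseline scores, clinical characteristics and race, and reads as exploratory. That figure is a worst case; 14 one-parameter terms give about 10%. However, several named predictors are multi-category or multi-item, the stated intention is the largest possible model, and nothing caps the subset models.
- **Other analyses do not depend on model size.** Chi-square comparisons are planned under hypotheses 1a and 2c, and race interactions appear under Aims 2 and 3. This limits the damage but does not correct the stated capacity.

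**Conclusion.** The stated capacity is wrong on the SAP's own rates. The limiting count is 154–184, not 312–342, and the convention that reproduces 30–35 then supports about 15–18 parameters overall and about 5–7 in the Black stratum.

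A reader might conclude that the arm effect for hypothesis 1a is seriously overstated. The documents do not support that: after the planned elimination the inflation is about 5% and type I error is near 5%.

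The material problem is the absence of any predictor limit for the race-stratified and communicator-arm models. In the Black stratum the likely distortion runs from about 10% inflation and 6% type I error (14 one-parameter terms) to about 11–17% and 7–9% (33 terms, after elimination).

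These sizes assume independent covariates, no clustering and enrolled patients only. The simulated arm coefficient stands for any binary term, since arm is not a predictor in the communicator-only model and is not named in the first Aim 3 model.

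**What to change.** In SAP section 6, hypothesis 1a, base the capacity on the number of patients without surgery, giving about 15–18 parameters in place of 30–35, and state the convention used. Pre-specify the starting model for hypothesis 1a within that limit, counting each category of a multi-category predictor as a parameter.

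For race questions under Aims 2 and 3, use race interactions in the pooled model, or a short pre-specified list of about 5–7 parameters within the Black stratum. Set a limit for the communicator-arm models in the same way. Label any larger model exploratory.

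The cost is SAP wording and fewer exploratory predictors in the main model.
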